6.8. Patient Disposition

Patient flow will be summarized from entered to randomized to completion, and analysis populations will be listed and summarized by treatment group.

The following patient disposition summaries will be provided for Open-Label Treatment Period (Period 2):

- The number and percentage of patients in the ITT population completing the Open-Label Treatment Period or prematurely discontinuing from the Open-Label Treatment Period, by treatment group and primary reason for discontinuation. Fisher's exact test will be used to test for treatment differences between treatment groups in the percentage of patients discontinuing from the Open-Label Treatment Period, and in the percentage of patients discontinuing for each reason.
- The number and percentage of patients in the ITT population completing the Open-Label Treatment Period or prematurely discontinuing from the Open-Label Treatment Period, by treatment group, visit, and primary reason for discontinuation.
- The time to discontinuation from the Open-Label Treatment Period due to any reason (in weeks).

Time to discontinuation due to any reason (in weeks) and due to an AE (in weeks) will be summarized graphically for the ITT population by treatment group using Kaplan-Meier techniques. The time to discontinuation (in weeks) from the Open-Label Treatment Period will be calculated as:

$$\frac{(\text{Date of discontinuation from Open-Label Treatment Period} - \text{Date of randomization} + 1)/7}$$

Patients completing the Open-Label Treatment Period will be censored at the date of completion (ie, the date of Visit 11 [Week 52]). Patients without a date of Open-Label Treatment Period completion or discontinuation will be censored at the last nonmissing date out of the following dates: date of last dose and date of last study visit up to and including Visit 11 (Week 52) (scheduled or unscheduled). Descriptive statistics including 25th percentile, median, 75th percentile, and corresponding 95% CIs, as well as probability of discontinuation by Week 52 will be summarized by treatment group. The log-rank test will be used to test for differences in the time to discontinuation between the treatment groups.

The following patient disposition summary will be provided for the Post-Treatment Follow-Up Period (Period 3):

- The number and percentage of patients in the Post-Treatment Follow-Up Population completing each follow-up visit or prematurely discontinuing from the Post-Treatment Follow-Up Period, by treatment group, visit, and primary reason for discontinuation.

Patient allocation by region, country, and center/site will be summarized with number of patients who entered the study, number of ITT patients for each treatment group, number of patients discontinued from study treatment, and number of patients discontinued from study.

6.9. Patient Characteristics

6.9.1. Demographics and Baseline Characteristics

Demographic variables and baseline characteristics (including baseline clinical measures) will be summarized for the ITT population. For weight, body mass index (BMI), tobacco use and alcohol consumption, baseline is defined in the same manner as the safety baseline (as defined in Section 6.15).

The continuous variables will be summarized using descriptive statistics, and the categorical variables will be summarized using frequency counts and percentages. The comparisons among treatment groups will be conducted using an ANOVA model with treatment as a factor for continuous data and using a Fisher's exact test for categorical data. (For categorical variables that have more than 2 categories, Monte Carlo estimates of exact p-values will be used.)

The demographic variables to be presented include the following:

- Age (in years)
- Age group: <65 years or ≥65 years
- Sex
- Age group within sex
- Ethnicity: Hispanic or Latino, Non-Hispanic and Non-Latino
- Race
- Country
- Geographic Regions:
 - Europe, Rest of the World
- Height (cm)
- Weight (kg)
- Weight category: <100 kg or ≥100 kg
- Weight category: <80 kg, ≥80 kg and <100 kg, or ≥100 kg
- Body mass index (BMI, kg/m²)
- Body mass index category (underweight (<18.5 kg/m²); normal (≥18.5 and <25 kg/m²); overweight (≥25 and <30 kg/m²); obese (≥30 and <40 kg/m²); or extremely obese (≥40 kg/m²)
- Tobacco use: never, current, or former
- Alcohol use: never, current, or former
- Other baseline characteristics to be presented include the following:
 - Time since PsA onset (years) – calculated as

$$(date\ of\ informed\ consent - date\ of\ PsA\ onset + 1) / 365.25$$

Patients who have a completely missing date of onset will have a missing value for the time since PsA onset, otherwise, “January” and “01” will be imputed for the missing month and day, respectively, in cases where these 2 date components are missing.

- Time since PsA diagnosis (years) – calculated as

$$(date\ of\ informed\ consent - date\ of\ PsA\ diagnosis + 1) / 365.25$$

Patients who have a completely missing date of diagnosis will have a missing value for the time since diagnosis, otherwise “January” and “01” will be imputed for the missing month and day, respectively, in cases where these 2 date components are missing.

- Time since PsA onset (years): <5 or ≥ 5
- Time since PsA diagnosis (years): ≤ 2 or >2
- Time since psoriasis (Ps) onset (years) – calculated as

$$(date\ of\ informed\ consent - date\ of\ Ps\ onset + 1) / 365.25$$

Patients who have a completely missing date of onset will have a missing value for the time since Ps onset, otherwise, “January” and “01” will be imputed for the missing month and day, respectively, in cases where these 2 date components are missing.

- Time since Ps diagnosis (years) – calculated as

$$(date\ of\ informed\ consent - date\ of\ Ps\ diagnosis + 1) / 365.25$$

Patients who have a completely missing date of diagnosis will have a missing value for the time since diagnosis, otherwise “January” and “01” will be imputed for the missing month and day, respectively, in cases where these 2 date components are missing.

- Tender Joint Counts (TJC) based on 68 joints
- Swollen Joint Counts (SJC) based on 66 joints
- Physician's global assessment of disease activity (mm)
- Patient's Global Assessment (PatGA) of Disease Activity (mm)
- Patient's assessment of joint pain (mm)
- Health Assessment Questionnaire–Disability Index (HAQ-DI) total score
- C-reactive protein (CRP) (mg/L)
- CRP categories; >6 mg/L or ≤ 6 mg/L
- Rheumatoid Factor Positive (RF+); yes or no
- Disease Activity Score-C-Reactive Protein (DAS28-CRP)
- DAS28-CRP; <2.6 , ≥ 2.6 and <3.2 , ≥ 3.2 and <5.1 , ≥ 5.1
- Enthesitis (LEI >0); yes or no
- Enthesitis (SPARCC >0); yes or no
- Leeds Enthesitis Index (LEI) for patients with baseline enthesitis (LEI >0)
- Spondyloarthritis Research Consortium of Canada (SPARCC) for patients with baseline enthesitis (SPARCC >0)
- Dactylitis (LDI-B score >0); yes or no
- Leeds Dactylitis Index – Basic (LDI-B) for patients with baseline dactylitis (LDI-B score >0)

- Modified CPDAI without the spinal disease assessment (Ankylosing Spondylitis Quality of Life Questionnaire [AsQoL] and BASDAI)
- Psoriasis Area and Severity Index (PASI) total score
- PASI total score: <12 , ≥ 12
- Static Physician Global Assessment of Psoriasis (sPGA) score
- sPGA score: <3 , ≥ 3
- Moderate to Severe Psoriasis (defined as PASI ≥ 12 , sPGA ≥ 3 , and BSA ≥ 10); yes or no
- Percentage of Body Surface Area (BSA)
- BSA: $<10\%$, $\geq 10\%$
- Itch Numeric Rating Scale (Itch NRS) score
- Itch NRS score; 0, >0 and ≤ 3 , >3
- Nail Psoriasis (NAPSI > 0): yes or no
- Nail Psoriasis Severity Index (NAPSI) score for patients with baseline fingernail involvement (NAPSI >0)
- Fatigue Severity Numeric Rating Scale (Fatigue NRS) score
- SF-36 Physical Component Summary score
- SF-36 Mental Component Summary score
- Dermatology Life Quality Index (DLQI) total score
- Columbia Suicide Severity Rating Scale (C-SSRS)
- Self-Harm Supplement Form
- Self-Harm Follow-Up Form
- Concomitant Glucocorticoids use at baseline; yes or no
- Concomitant Glucocorticoids mean daily dose at baseline
- Concomitant Methotrexate use at baseline; yes or no
- Concomitant Methotrexate mean weekly dose at baseline
- Concomitant Conventional disease-modifying antirheumatic drugs (csDMARD) use at baseline; yes or no
- Number of prior csDMARD therapies: 1, 2, 3, or >3
- European Quality of Life – 5 dimensions 5 level (EQ-5D 5L)
- Latent TB; yes or no.

By-patient listings of demographic and baseline characteristics, respectively, for the ITT population will be provided.

6.9.2. Previous Therapy for Psoriatic Arthritis

The number and percentage of patients who received previous therapy for PsA (as recorded on the *Previous Therapy: Psoriatic Arthritis* electronic case report form [eCRF] page) will be summarized by treatment group, overall, and preferred name. The number and percentage of patients with each reason for discontinuing previous therapy for PsA will also be presented by treatment group.

Previous therapy for PsA will be summarized for the ITT population.

Treatment group comparisons for the ITT population will be conducted using Fisher's exact test.

Listing of previous therapy for PsA will be provided for the ITT population.

6.9.3. Historical Illness and Pre-existing Conditions

Historical illnesses and pre-existing conditions will be classified using the latest version of the Medical Dictionary for Regulatory Activities (MedDRA) dictionary. Historical illness/condition is defined as the condition/event recorded on the *Pre-Existing Conditions and Medical History* eCRF page or on the *Prespecified Medical History* eCRF page with an end date prior to the date of informed consent. Pre-existing conditions for the Open-Label Treatment Period (Period 2) are defined as those conditions recorded on the *Pre-Existing Conditions and Medical History* eCRF page or on the *Prespecified Medical History* eCRF pages with a start date prior to the date of informed consent, and no end date (ie, the event is ongoing) or an end date after the date of informed consent. Adverse events occurring prior to the date of first study injection will also be reported for the open-label treatment period (Period 2). If a pre-existing condition worsens in severity on or after the date of informed consent, it will be considered an AE from the date of worsening onwards. Patients will only be counted once, regardless of how many conditions are included under the same System Organ Class (SOC) and Preferred Term (PT).

The number and percentage of patients with historical illnesses, pre-existing conditions and adverse events occurring prior to the first dose will be provided by treatment group, overall, and by SOC and PT for the Open-Label Treatment Period for the ITT population. For condition/event that is gender specific (as defined by MedDRA), the denominator and computation of the percentage will include only patients from the given gender.

Treatment group comparisons for ITT population will be conducted using Fisher's exact test.

Listing of historical illnesses and pre-existing conditions will be provided for ITT population.

6.10. Treatment Compliance

Study treatment dispensed will be listed (including the CT Lot number) for all entered patients. Study treatment administration and compliance will be listed for all entered patients.

Patients will record information in a Study Drug Administration Log (captured in the *Exposure* eCRF page), including the date, time, and anatomical location of administration of investigational product, syringe number, who administered the investigational product, and the reason if the investigational product was not fully administered.

Treatment compliance (%) for each patient will be calculated as:

$$100 \times \frac{\text{Total number of injections administered}}{\text{Total number of injections prescribed}}$$

- Number of injections prescribed (that is, expected) is 17 injections for patients on ixekizumab with moderate-to-severe plaque psoriasis. Patients will receive 2 ixekizumab 80 mg injections at Week 0, 1 ixekizumab 80 mg injection every 2 weeks from Week 2 to Week 12, and 1 ixekizumab 80 mg injection every 4 weeks from Week 16 to Week 48.

- Number of injections prescribed (that is, expected) is 14 injections for patients on ixekizumab without moderate-to-severe plaque psoriasis. Patients will receive 2 ixekizumab 80 mg injections at Week 0 and 1 ixekizumab 80 mg injection every 4 weeks from Week 4 to Week 48.
- Number of injections prescribed (that is, expected) is 28 injections for patients on adalimumab with moderate-to-severe plaque psoriasis. Patients will receive 2 adalimumab 40 mg injections at Week 0 and 1 adalimumab 40 mg injection every 2 weeks from Week 1 to Week 51.
- Number of injections prescribed (that is, expected) is 26 injections for patients on adalimumab without moderate-to-severe plaque psoriasis. Patients will receive 1 adalimumab 40 mg injection every 2 weeks from Week 0 to Week 50.
- For patients who discontinue during Period 2, the number of injections prescribed can be derived from the IWRS study drug dispense dataset.
- The total number of injections administered will be derived using the response to the question, “Was dose administered?” on the *Exposure* eCRF page.

Overall compliance for the Open-Label Treatment Period will be considered if the patient misses no more than 20% of the expected doses, does not miss 2 consecutive doses, and does not overdose (that is, take more injections at the same time point than specified in the protocol) within the study period.

Treatment compliance with investigational product will be summarized for the Open-Label Treatment Period (ITT population).

Treatment group comparisons will be conducted for the ITT population using a Fisher’s exact test.

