6.18. Interim Analyses and Data Monitoring

An interim database lock will occur, and the analysis will be performed at the time (that is, a cutoff date) when the last patient completes Visit 8 (Week 24), completes ETV, or discontinues from Period 2. This database lock will include all data collected by the cutoff date including data after Week 24 from the Open-Label Treatment Period and follow-up data from patients who have begun Post-Treatment Follow-Up Period (Period 3).

This interim database lock at Week 24 will be considered the primary database lock for this study because all primary and major secondary study objectives will be assessed at this time.

A final database lock will occur after all enrolled patients have completed or discontinued the Post-Treatment Follow-Up Period.

There will be no data monitoring committee.

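### Discontinuers' expected injections come from dispensing data with no cut at the stop date, so fully adherent patients, mostly on adalimumab, can be scored noncompliant

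*SAP*

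**What the plan says.** SAP 6.10 defines percent compliance as 100 times injections administered divided by injections prescribed, and treats prescribed as meaning expected. Four fixed totals cover the 52-week period:

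- "Number of injections prescribed (that is, expected) is 17 injections for patients on ixekizumab with moderate-to-severe plaque psoriasis"
- "Number of injections prescribed (that is, expected) is 14 injections for patients on ixekizumab without moderate-to-severe plaque psoriasis"
- "Number of injections prescribed (that is, expected) is 28 injections for patients on adalimumab with moderate-to-severe plaque psoriasis"
- "Number of injections prescribed (that is, expected) is 26 injections for patients on adalimumab without moderate-to-severe plaque psoriasis"

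The only exception is for patients who stop during Period 2, for whom "the number of injections prescribed can be derived from the IWRS study drug dispense dataset". A patient is compliant overall if he or she "misses no more than 20% of the expected doses, does not miss 2 consecutive doses, and does not overdose", so failing any one of the three conditions makes the patient noncompliant. The arms are compared by Fisher's exact test.

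Three other places bear on the point. Protocol 10.3.2.4 promises the comparison by visit as well as overall. SAP 6.17, Table RHCF.6.9, lists noncompliance as an important violation, but there the patient must both miss more than 20% of doses and miss two or more in a row. SAP 6.18 states: "This interim database lock at Week 24 will be considered the primary database lock for this study".

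**The concern.** A dispensing record shows what the patient was given to last until the next visit. It does not show what had fallen due when treatment stopped. If dispensed injections are the denominator, a patient who took every dose on time and stopped between visits is charged with the unused syringes. Ixekizumab is given every 4 weeks for most of the study and adalimumab every 2 weeks, so the charge is heavier on adalimumab. The compliance comparison could then show a difference between arms that reflects dosing frequency, not behaviour. SAP 6.17 also plans additional analyses of the primary and/or major secondary endpoints in patients free of all, or of some, violations. If compliance is among those chosen, adherent patients would be removed unequally.

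A second gap concerns patients still on treatment at a data cut: 6.10 gives them no reduced count.

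**Working it through.** **Inputs.** Dosing weeks are from protocol Table RHCF.2.1. Dispensing visits are Weeks 0, 4, 8, 12, 16, 24, 32 and 40 (protocol Section 2). Protocol 7.1.2 says cartons match the planned dispensing schedule but gives no quantities. I assume supply up to the next dispensing visit and no spares. The completion rate is 72% (protocol 5.2). Injections are counted, as in the SAP formula.

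**The plan's totals reproduce.**

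- Ixekizumab, moderate-to-severe psoriasis: 2 at Week 0 + 6 (Weeks 2–12) + 9 (Weeks 16–48) = 17.
- Ixekizumab, other: 2 + 12 (Weeks 4–48) = 14.
- Adalimumab, moderate-to-severe: 2 + 26 (Weeks 1–51) = 28.
- Adalimumab, other: 26 (Weeks 0–50).

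**Single stop times**, fully adherent, without moderate-to-severe psoriasis, taken/dispensed:

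| Stop | Ixekizumab | Adalimumab |
|---|---|---|
| Week 1 | 2/2 = 100% | 1/2 = 50% |
| Week 5 | 3/3 = 100% | 3/4 = 75% |
| Week 17 | 6/7 = 86% | 9/12 = 75% |
| Week 25 | 8/9 = 89%, 1 unused | 13/16 = 81%, 3 unused in a row |

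At Week 25 the adalimumab patient passes the 20% condition and fails the consecutive-dose condition.

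**All stop times.** Each cell gives the number of weeks in the supply interval during which a fully adherent patient who stops is flagged by either condition. The 20% condition alone is in brackets.

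| Interval (weeks) | IXE mod-sev | IXE other | ADA mod-sev | ADA other |
|---|---|---|---|---|
| 0–4 | 2 (2) | 0 (0) | 3 (3) | 2 (2) |
| 4–8 | 0 (0) | 0 (0) | 1 (1) | 2 (2) |
| 8–12 | 0 (0) | 0 (0) | 1 (1) | 0 (0) |
| 12–16 | 0 (0) | 0 (0) | 1 (0) | 0 (0) |
| 16–24 | 0 (0) | 0 (0) | 5 (3) | 4 (2) |
| 24–32 | 0 (0) | 0 (0) | 5 (1) | 4 (0) |
| 32–40 | 0 (0) | 0 (0) | 5 (0) | 4 (0) |
| 40–52 | 4 (0) | 4 (0) | 9 (1) | 8 (0) |
| Sum | 6 (2) | 4 (0) | 30 (10) | 24 (6) |
| Sum/52 | 11.5% (3.8%) | 7.7% (0%) | 57.7% (19.2%) | 46.2% (11.5%) |

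The last row is the share flagged if stop times are uniform over 52 weeks. The consecutive-dose condition supplies most of the gap.

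**Share of the arm.** With 28% discontinuing in each arm: ixekizumab 0.28 × 7.7% = 2.2% to 0.28 × 11.5% = 3.2%; adalimumab 0.28 × 46.2% = 12.9% to 0.28 × 57.7% = 16.2%. The range is the psoriasis mix.

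**Table RHCF.6.9 definition.** Requiring both conditions flags 0% of adherent ixekizumab discontinuers, and 2/52 = 3.8% (other) to 8/52 = 15.4% (moderate-to-severe) on adalimumab.

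**Patients ongoing at a cut, 52-week totals used unchanged.** At exactly Week 24, with that week's dose taken, full adherence scores 11/17 = 64.7% and 8/14 = 57.1% on ixekizumab, and 14/28 = 50.0% and 13/26 = 50.0% on adalimumab. The score first reaches 80% at Weeks 36 and 40 (ixekizumab) and Weeks 41 and 40 (adalimumab), moderate-to-severe first. Fewer than two doses remain from Week 44 in both ixekizumab regimens, and from Weeks 49 and 48 on adalimumab.

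**The case against.** The wording for discontinuers is permissive. A programmer could use dispense dates to work out which doses were due, and a dose not yet due is not naturally a missed one. That is fair: this is a rule left unspecified, not a fixed instruction to divide by syringes issued. But 6.10 equates prescribed with expected, names dispensing as the source and gives no cut, so following it at face value produces the error. A comparison tested between open-label arms should not depend on a programming choice.

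The size depends on assumptions. Weeks 1, 5 and 17 fall in the only windows (Weeks 0–2, 4–6 and 16–18) where an adherent adalimumab patient without moderate-to-severe psoriasis drops below 80%. If patients stop at scheduled visits before new supply is issued, nothing is miscounted. Both points stand, and most adherent ixekizumab discontinuers are not flagged on any of these assumptions.

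A reader might infer that every patient still on treatment at the primary lock would be scored noncompliant. The documents do not support that. SAP 6.18 sets the cutoff when the last patient reaches Week 24, so earlier enrollees are further along and may pass. Nor does any section say that compliance is reported at that lock. The totals 17/14/28/26 are right for completers.

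It is also tempting to read protocol 7.6 as requiring withheld doses to be removed from the denominator. It asks only that necessary interruptions be taken into account when noncompliance is judged.

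**Conclusion.** The concern holds in limited form. SAP 6.10 lets doses that were never due count as missed for discontinuers, and the effect falls mainly on adalimumab: about 46–58% of fully adherent discontinuers flagged, against 8–12% on ixekizumab (12–19% against 0–4% on the 20% condition alone). At arm level this is about 13–16% against 2–3%. These figures assume supply to the next dispensing visit, no spare syringes, uniform stop times and 28% discontinuation in each arm. The lower bound is zero in both arms.

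If 6.10 were also run unchanged on the Week 24 cut, which the documents do not state, every adherent ongoing patient before about Week 36 would fall below 80%.

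A reader might infer a threat to the trial's main conclusions. There is none: the primary and major secondary tests use the ITT population with nonresponder imputation, and compliance does not enter them. The consequences stop at the compliance comparison, the compliance listing and possibly the violation-free supportive analyses. That last route is narrower because Table RHCF.6.9 requires both conditions, and because SAP 6.17 does not say which violations will be used.

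**What to change.** In SAP 6.10, define expected injections for every patient and any data cut as those scheduled in Table RHCF.2.1 from Week 0 to the earliest of treatment discontinuation, data cutoff or Week 52. Keep 17/14/28/26 as the resulting totals for completers. Fully adherent patients then score 100% in all four regimens, and the same rule supplies the by-visit denominator that protocol 10.3.2.4 needs and 6.10 lacks. State how treatment interruptions are taken into account, consistent with protocol 7.6. Reconcile the noncompliance definition in Table RHCF.6.9, where both conditions must be met, with 6.10, where failing one is enough.

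The cost is a short change to the SAP wording and minor programming, with no new data collection.

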7.6. Treatment Compliance

Every attempt will be made to select patients who have the ability to understand and comply with study instructions. The investigator is responsible for discussing methods to ensure high treatment compliance with the patient before randomization.

Randomized patients will record the date and time of administration of investigational product in a Study Drug Administration Log throughout their participation in the study. The data from the Study Drug Administration Log must be transcribed into the eCRF by site personnel.

Patient compliance with study medication will be assessed at each visit. Compliance will be assessed by review of the Study Drug Administration Log, return of empty investigational product packaging, and/or direct questioning.

The patient should be instructed to retain all empty study drug packaging after using up the medication and to bring the empty packaging and any unused medication to the study site at each visit, so that the site staff can record the amount of medication used since the last visit. Deviation(s) from the prescribed dosage regimen should be documented.

If a patient is noncompliant with study procedures and/or study drug administration, the investigator should assess the patient to determine the reason for noncompliance and educate and/or manage the patient as appropriate to improve compliance. If, in consultation with Lilly or its designee, the noncompliance is deemed to be significant or if further noncompliance occurs, the patient should be discontinued from the study (see Section 10.3.2.4 Treatment Compliance).

In some circumstances, it may be necessary to temporarily interrupt treatment (see Section 8.1.2 and Section 9.4.5). Any necessary interruption of treatment should be considered when determining noncompliance.

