8.1.2. Temporary Discontinuation from Study Treatment

In some circumstances, it may be necessary to temporarily interrupt treatment as a result of abnormal laboratory values (see Section 8.1.1), AEs (see Section 9.2), hypertension (see Section 9.4.5.1) abnormal hepatic laboratory values (see Section 9.4.5.2), neutropenia (see Section 9.4.5.3), hepatitis B laboratory findings (see Section 9.4.5.4), or inflammatory bowel disease (IBD) events (see Section 9.2.1.1) that may have an unclear relationship to investigational product. See Section 9.4.4.2 for details regarding managing patients who test positive for TB at any time during the study.

Patients requiring surgery at any time during the study should interrupt administration of the investigational product beginning 8 weeks before the surgery, or as early as possible within 8 weeks of surgery, and resume administration of the investigational product only after complete wound healing.

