9.4.5.3. Neutropenia

Patients with neutrophil counts <1500 cells/μL should be managed for neutropenia as follows:

- <500 cells/µL, see Discontinuation Criteria (Section 8.1.1)
- \geq 500 cells/ μ L and <1000 cells/ μ L, see Discontinuation Criteria (Section 8.1.1)
- ≥1000 cells/μL and <1500 cells/μL (based on 3 test results), and the patient has a concurrent infection that requires systemic anti-infective therapy (for example, antibiotic, antifungal agent, antiviral agent):
 - The dose of investigational product should be withheld, the patient should receive appropriate medical care, and a repeat test for neutrophil count should be performed within 4 weeks from knowledge of the initial report. If the repeat neutrophil count has returned to $\geq\!1500$ cells/µL and the infection has resolved or is resolving, the patient may resume dosing of investigational product and evaluation at scheduled visits. If the neutrophil count remains $\geq\!1000$ cells/µL and $<\!1500$ cells/µL, investigational product should continue to be withheld and a repeat neutrophil count should again be performed within another 4 weeks. If, after 2 repeat tests, the neutrophil count still remains $\geq\!1000$ cells/µL and $<\!1500$ cells/µL, and:
 - a. the infection has not fully resolved, the patient will be discontinued from the study.
 - b. the infection has resolved, the patient may resume dosing and evaluation at scheduled visits. However, if resumption of dosing is not deemed appropriate by the investigator, the patient will be discontinued from the study.
- ≥1000 cells/μL and <1500 cells/μL (based on 3 test results), and the patient has no concurrent infection that requires systemic anti-infective therapy (for example, antibiotic, antifungal agent, antiviral agent):

 Dosing may continue, and a repeat neutrophil count should be performed 4 to 8 weeks from knowledge of the initial report. Testing may be at a regularly scheduled visit or at an unscheduled visit, as necessary.

Repeat testing should be performed at 4- to 8-week intervals until the neutrophil count has returned to $\geq\!1500$ cells/ μL . If the patient has 3 or more postbaseline neutrophil counts of $\geq\!1000$ cells/ μL and $<\!1500$ cells/ μL , no value of $<\!1000$ cells/ μL , and no postbaseline infection requiring systemic anti-infective therapy, the patient may continue or resume further evaluation at scheduled visits, as deemed appropriate by the investigator.

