10.3.2.4. Treatment Compliance

Treatment compliance with investigational product will be summarized for patients who enter Period 2. A patient will be considered compliant overall to ixekizumab or adalimumab if he/she is missing no more than 20% of the expected doses, does not miss 2 consecutive doses, and does not double-dose (that is, take more injections at the same time point than specified in the protocol). Proportions of patients compliant by visit and overall will be compared between treatment groups during Period 2 using Fisher's exact test.

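### SAP 6.10 has no step for protocol-directed dose holds, so compliance and its between-arm test mix nonadherence with holds and depend on dosing interval

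*SAP*

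**What the plan says.** **The instruction.** Protocol 7.6 points to the interruptions in Sections 8.1.2 and 9.4.5 and then states: "Any necessary interruption of treatment should be considered when determining noncompliance".

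**The holds.**
- Protocol 8.1.2: patients who need surgery "should interrupt administration of the investigational product beginning 8 weeks before the surgery", or as early as possible within that window, and resume only after wound healing.
- Protocol 9.4.5.3: for neutrophils of 1000 to <1500 cells/µL with an infection needing systemic treatment, the dose is withheld and the count repeated within 4 weeks. If it has not recovered, "investigational product should continue to be withheld and a repeat neutrophil count should again be performed within another 4 weeks".
- Protocol 9.4.5.1: withholding is one option for hypertension, with no stated length.

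**The compliance rule.** Under SAP 6.10 a patient is compliant if he or she "misses no more than 20% of the expected doses, does not miss 2 consecutive doses, and does not overdose". Protocol 10.3.2.4 has the same criteria: "missing no more than 20% of the expected doses, does not miss 2 consecutive doses, and does not double-dose". In SAP 6.10 the expected number "is 17 injections for patients on ixekizumab with moderate-to-severe plaque psoriasis", "is 14 injections for patients on ixekizumab without moderate-to-severe plaque psoriasis" and "is 28 injections for patients on adalimumab with moderate-to-severe plaque psoriasis"; it is 26 for the other adalimumab patients. Only early discontinuation changes these totals. Injections given are counted from the Exposure eCRF item asking whether the dose was administered.

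**The uses.** SAP 6.10 compares compliance between arms with Fisher's exact test in the ITT population. Table RHCF.6.9 has a separate compliance flag for important protocol violations, and SAP 6.17 plans analyses of the primary and/or major secondary endpoints in patients without some or all violations.

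**The concern.** The protocol's general instruction is put into effect nowhere. With a fixed denominator, a numerator that counts only administered doses, and no exception, a dose withheld on the protocol's own direction is scored like a dose the patient skipped.

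The consecutive-dose clause counts doses, not time. Two consecutive doses span 4 weeks on Q2W dosing and 8 weeks on Q4W dosing, so the same hold can be judged differently in the two arms. In an open-label head-to-head trial, a between-arm compliance difference could then be read as patient behaviour when part of it comes from the dosing interval.

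**Working it through.** **1. The plan's totals.** Counting the calendar in Table RHCF.2.1:
- ixekizumab, moderate-to-severe psoriasis: 2 + 6 (Weeks 2-12, Q2W) + 9 (Weeks 16-48, Q4W) = 17
- ixekizumab, others: 2 + 12 = 14
- adalimumab, moderate-to-severe psoriasis: 2 + 26 (Weeks 1-51) = 28
- adalimumab, others: 26 (Weeks 0-50)

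All four agree with SAP 6.10.

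**2. Method.** A hold of fixed length was placed at every start day after Day 0 that fits the treatment period. The hold includes its first day but not the day dosing may resume. Scheduled doses inside it were counted as not given, no other dose was missed, and percent missed = doses in hold / expected injections. A patient fails SAP 6.10 if more than 20% are missed or 2 consecutive doses are missed. Table RHCF.6.9 flags a patient only if both apply.

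**3. Full 4-week hold (336 start days).**

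| Regimen | Doses missed | Given | Start days failing SAP 6.10 |
|---|---|---|---|
| Adalimumab (26) | 2 | 24/26 = 92.3% | 336/336 |
| Adalimumab (28) | 2 | 26/28 = 92.9% | 336/336 |
| Ixekizumab Q4W (14) | 1 | 13/14 = 92.9% | 0/336 |
| Ixekizumab Q2W/Q4W (17) | 2 in the Q2W phase, otherwise 1 | 15/17 = 88.2% or 16/17 = 94.1% | 70/336 = 20.8% |

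If both end days of the hold are counted, ixekizumab Q4W fails at 11/336 = 3.3% of start days. No regimen reaches the Table RHCF.6.9 flag.

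**4. Full 8-week hold (308 start days).**

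| Regimen | Missed | Fails SAP 6.10 | Meets the Table RHCF.6.9 flag |
|---|---|---|---|
| Adalimumab (26) | 4/26 = 15.4% | 308/308 | 0 |
| Adalimumab (28) | 4/28 = 14.3% | 308/308 | 0 |
| Ixekizumab Q4W (14) | 2/14 = 14.3% | 308/308 | 0 |
| Ixekizumab Q2W/Q4W (17) | 2/17 = 11.8% to 4/17 = 23.5% | 308/308 | 42/308 = 13.6% |

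Except where 4 of 17 are missed, every failure is on the consecutive-dose clause alone. Counting both end days, ixekizumab Q4W meets the flag at 3.2% of start days.

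**5. Shorter and longer holds.** A 3-week hold fails adalimumab at 49.0% (26-injection) or 51.0% (28-injection) of start days, ixekizumab Q4W at none, and ixekizumab Q2W/Q4W at 10.2%. A 2-week hold fails no regimen. A 12-week hold (8 weeks plus an assumed 4 for healing) misses 6/26 = 23.1%, 6/28 = 21.4% or 3/14 = 21.4%, so it meets the Table RHCF.6.9 flag at every start day in those three regimens. In the 17-injection regimen it does so at 25.0% of start days.

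**6. With the exclusion.** If withheld doses leave both the expected count and the consecutive-dose check, a patient whose only gap is the hold has no missed doses in any regimen, and the arm difference disappears.

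**The case against.** The strongest reply is that SAP 6.10 never says a withheld dose is a missed dose. It records why a product was not fully administered and lists compliance by patient, so a programmer aware of Protocol 7.6 could handle holds sensibly. That stands as far as it goes: the scoring is inferred from the fixed totals, the administered-dose numerator and the absence of an exception. But an instruction left to the programmer is not prespecified, and following the text gives the results above.

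Other limits also stand:
- The surgery hold may start later than 8 weeks before, and 4 weeks is the maximum for the first neutropenia step. A reader might infer that everyone who follows either hold is noncompliant; shorter holds may pass.
- A reader might infer that a 4-week hold counts only against adalimumab. It also fails ixekizumab patients dosing Q2W in Weeks 2-12.
- Protocol 7.2.1 has missed doses given as soon as possible. If that extends to withheld doses, some would count as administered and the effect would soften.
- Entry criteria exclude neutrophils below 1500 cells/µL and joint surgery expected up to Week 24, which makes holds less frequent.
- The gap is not only in the SAP: Protocol 10.3.2.4 has the same criteria, so the mismatch begins inside the protocol.

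**Conclusion.** The point holds as a defect in a secondary summary and should be corrected. The compliance rule does not carry out Protocol 7.6, and the Fisher comparison therefore mixes nonadherence with protocol-directed holds in a way that depends on dosing interval. This assumes that withheld doses are scored as not given, are not made up later, and that the hold runs its full 4 or 8 weeks. The documents do not give the number of patients with holds, so the size of any arm difference cannot be stated.

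Two stronger readings are not supported. The first is that the same rule drives the protocol-violation flag. Table RHCF.6.9 requires more than 20% missed and 2 or more consecutive missed doses, so in practice only holds longer than 8 weeks, or those in the ixekizumab Q2W phase, reach it and could affect the violation-free analyses. The two definitions do contradict each other. The second is that the main results are biased: the primary and major secondary analyses use the ITT population with nonresponder imputation and do not use compliance.

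**What to change.** In SAP 6.10, and by cross-reference in Protocol 10.3.2.4, exclude doses documented as withheld under Protocol 8.1.2 or 9.4.5 from both the expected count and the consecutive-dose check, using the recorded reason for non-administration. Those are the sections Protocol 7.6 itself cites, although they include some discretionary holds. Withheld doses should therefore be tabulated by arm so the exclusion is visible. State also whether ordinary misses on either side of a hold count as consecutive.

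Reconcile the Table RHCF.6.9 definition with SAP 6.10 and apply the same exclusion there.

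The cost is a sentence or two in each document, a programming step and one table. The downside is reliance on accurate coding of the reason a dose was not given. No change to the clinical hold rules is proposed.
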